#### 16.1.8. Determination of Sample Size

The planned sample size of at least 3 subjects at each dose schedule was considered sufficient to assess and to detect major safety and tolerability problems.

#### **17. REGULATORY, ETHICAL AND LEGAL OBLIGATIONS**

#### **17.1. DECLARATION OF HELSINKI**

The study will be conducted in accordance with the Declaration of Helsinki and GCP according to International Conference on Harmonisation (ICH) guidelines. Specifically, the study will be conducted under a protocol reviewed by an IRB or IEC; the study will be conducted by scientifically and medically qualified persons; the PI and Sponsor believe the benefits of the study are in proportion to the risks; the rights and welfare of the subjects will be respected; and all the physicians conducting the study do not find the hazards to outweigh the potential benefits; and each subject will give his or her written, informed consent in their native language before any protocol-driven tests or evaluations are performed. Consent to serial biopsies will be asked for separately from the consent to participate in the study. This consent must also be written and in the native language of the subject. A subject can consent to the study and not consent to the serial biopsies and will not be excluded for not consenting to the biopsies.

#### **17.2.** INSTITUTIONAL REVIEW BOARDS/ETHICS COMMITTEES

The Investigator will submit this protocol to the appropriate Independent Ethics Committee/Institutional Review Board (IEC/IRB) and will maintain a record of IEC/IRB review/approval at the site. During the clinical trial, any amendment or modification to the protocol will be sent to the IEC/IRB. The IEC/IRB will also be informed of any event likely to affect the safety of subjects or the continued conduct of the study, in particular any change in safety and all updates to the Investigator's Brochure will be sent to the IEC/IRB.

The IEC/IRB will approve all protocol amendments, written informed consent documents and document updates, subject recruitment procedures, written information to be provided to the subjects, available safety information, information about payment and compensation available to subjects, the investigator's curriculum vitae and/or other evidence of qualifications, and any other documents requested by the IEC/IRB and regulatory authority, as applicable.

## **17.3.** ETHICAL CONDUCT OF THE STUDY

The investigator is responsible for ensuring that the clinical study is conducted in accordance with the protocol and to Standard Operating Procedures (SOPs), Food and Drug Administration (FDA) Good Clinical Practice (GCP) guidelines, FDA Financial Disclosure regulations, as well as the ICH guidelines and any other regional/national requirements for clinical trials, as applicable.

#### **17.4. PROTOCOL AMENDMENTS**

Any amendment to the protocol requires written approval/favorable opinion by the IEC/IRB prior to its implementation, unless there are overriding safety reasons.

In some instances, an amendment may require a change to the Informed Consent Form. The Investigator will obtain an IEC/IRB approval/favorable opinion concerning the revised Informed Consent Form prior to implementation of the change. The investigator understands that subjects must be consented using the most current IEC/IRB approved version of the Informed Consent Form. If the Informed Consent Form is updated, subjects who are still receiving therapy will be re-consented, or at the direction of the IEC/IRB.

#### **17.5.** COMPLIANCE WITH THE PROTOCOL AND PROTOCOL REVISIONS

The investigator must comply with all requirements of the protocol. When a situation occurs that requires a temporary departure from the protocol, the Investigator or other physician in attendance should contact the sponsor or designee as soon as possible in order to discuss the situation and agree on an appropriate course of action. The investigator will describe the departure from the protocol and the circumstances requiring it on the CRF/eCRF and will notify the IRB/IEC as appropriate.

#### **17.6.** INFORMED CONSENT

The investigator or his/her designee will inform the subject of all aspects pertaining to their participation in the study. The process for obtaining subject informed consent will be in accordance with all applicable regulatory requirements (e.g., CFR Part 50 and ICH E6 Section 4.8).

Prior to the beginning of the study, the investigator must have the IRB/IEC's written approval/favorable opinion of the written informed consent form and any other information to be provided to the subjects.

The subject must have been given a copy of the informed consent form (ICF) at least 24 hours prior to being asked to sign the document. The investigator or his/her designee and the subject must both sign and date the ICF before the subject can participate in the study. The subject will receive a copy of the signed and dated form, and the original will be retained in the site's study records. The decision to participate in the study that is made by the subject must be entirely voluntary. The investigator or his/her designee must emphasize to the subject that consent for study participation may be withdrawn at any time without penalty or loss of benefits to which the subject is otherwise entitled.

The informed consent and any other information provided to subjects or the subject's legally acceptable representative should be revised whenever important new information becomes available that is relevant to the subject's consent and should receive IRB/IEC approval/favorable opinion prior to use. The investigator, or a person designated by the investigator, should fully inform the subject or the subject's legally acceptable representative of all pertinent aspects of the study and of any new information relevant to the subject's willingness to continue participation in the study. This communication should be documented. During a subject's participation in the trial, any updates to the consent form and any updates to the written information will be provided to the subject.

#### **17.7.** CONFIDENTIALITY AND DISCLOSURE

Confidentiality will be maintained within legal limits in the review of the medical records and consent forms, which may contain the identity of the subject. All subjects' identities will be restricted to their initials and a unique subject number.

Regulatory agencies or ethics committees may review medical records, and other study documentation for auditing or inspection purposes. Investigators and their affiliated institutions that are considered covered entities (CE) under the Health Insurance Portability and Accountability Act (HIPAA) will request that the subject sign a fully informed Authorization that will accompany the consent form. The Authorization will include the Authorization Core Elements (see Privacy Rule, 45 CFR §164.508(c)(1)) and the Authorization Required Statements (see Privacy Rule, 45 CFR §164.508(c)(2)). These activities are intended to ensure that subjects understand how their Protected Health Information (PHI) arising from this research study is to be handled. The Privacy Rule is an additional but similar obligation to those that have been required under the Department of Health and Human Services (DHHS) or the Food and Drug Administration (FDA) Protection of Human Subjects Regulations (e.g., 45 CFR part 46 or 21 CFR parts 50 and 56, respectively) to take measures to protect such PHI from inappropriate use or disclosure.

The investigator and other study site personnel will keep confidential any information (including this protocol) related to this study and all data and records generated in the course of conducting the study, and will not use the information, data, or records for any purpose other than conducting the study. These restrictions do not apply to (1) Information that becomes publicly available through no fault of the investigator or study site personnel; (2) information that it is necessary to disclose in confidence to an IRB/IEC solely for the evaluation of the study; (3) information that it is necessary to disclose in order to provide appropriate medical care to a study subject; or (4) study results that may be published as described under the Publication Section.

#### **17.8.** MONITORING AND AUDITING STUDY DOCUMENTATION

The Sponsor (or designee) of this study is responsible to Health Authorities for taking all reasonable steps to ensure the proper conduct of the study in regards to ethics, protocol compliance, and integrity and validity of the data recorded on the CRFs. The Sponsor is also responsible for monitoring data quality and subject safety. Thus, the main duty of the Sponsor is to help the investigator to maintain a high level of ethical, scientific, technical and regulatory quality in all aspects of the study.

For the purposes of ensuring compliance with the protocol, GCP, and applicable regulatory requirements, the investigator will permit monitoring and auditing by the Sponsor or designee and inspection by applicable regulatory authorities.

The investigator agrees to allow the auditors/inspectors to have direct access to his/her study records for review, being understood that these personnel are bound by professional secrecy, and as such will not disclose any personal identity or personal medical information.

The confidentiality of the data verified and the anonymity of the subjects should be respected during these inspections.

# **17.9.** Study Report, Publication Policy and Archiving of Study Documentation

All data and records generated during the study and all inventions discovered in the course of conducting the study are the property of Immunovative Therapies, Ltd.

Immunovative Therapies, Ltd. will retain ownership of all data. Data derived from the trial are the exclusive property of Immunovative. All proposed publications based on this study will be subject to the Sponsor's approval requirements. Any publication or presentation related to the trial must be reviewed and approved by the Sponsor before submission of the manuscript. If the Sponsor publishes a manuscript, each PI and sub-investigator (as appropriate) will be named as an author and will have an opportunity to review and approve the submission of the manuscript.

The investigator (or designee) will be responsible for preparing the Clinical Study Report for the site. An integrated clinical study report for all sites will be prepared by the Sponsor in accordance with ICH E3 guidance.

#### **17.10. DATA CAPTURE**

#### 17.10.1. Case Report Forms

The CRF is an integral part of the study and subsequent reports. The CRF must be kept current to reflect subject status during the course of the study. Only the subject number and an alpha code will be used to identify the subject.

After obtaining written source document information from each subject at each visit, the site will enter the data onto a paper CRF or directly into an internet –based data collection system (as described under section 11.50.2; Electronic Data Capture).

Source documents are where subject data are recorded and documented for the first time. They include, but are not limited to hospital records, clinical and office charts, laboratory notes, evaluation checklists, pharmacy dispensing records, recorded data from automated instruments, copies of transcriptions that are certified after verification as being accurate and records kept at the pharmacy, laboratories, and other departments involved in a clinical trial.

Source documents that are required to verify the validity and completeness of data transcribed on the CRFs must never be obliterated or destroyed.

The investigator will maintain a Delegation of Authority Page to document all persons authorized to make entries and/or corrections on CRFs. The CRF should be reviewed, signed, and dated by investigator.

In case of paper CRF, all CRFs should be completed in a neat, legible manner to ensure accurate interpretation of data. Black ink is required to ensure clarity of reproduced CRF copies. When making changes or corrections, original entries will be crossed out with a single line, and the changes will be initialed and dated. DO NOT ERASE, OVERWRITE OR USE CORRECTION FLUID ON THE ORIGINAL CRF ENTRY.

According to the GCP guidelines, the investigator (or designee) will check the CRF entries against the source documents, except for the pre-identified source data directly recorded in the CRF.

The following table identifies what are source vs. CRF data in this study:

| Type of Data   | Source/CRF  | Comment   |
|--|---|---|
| Informed consent   | Source documents  | Signature date is captured on CRF   |
| Demographics   | Source documents and CRF                                  |   |
| Inclusion/Exclusion  | Source documents and                                      |   |
| Criteria   | CRF   |   |
| Medical History (incl.   | Source documents and                                      |   |
| Disease History)   | CRF   |   |
| Physical Examination   | Source documents  | Performance date and clinically
significant results are documented on
CRF |
| Vital Signs  | Source documents  | Performance date and clinically
significant results are documented on
CRF |
| ECOG   | Source documents and CRF                                  |   |
| EKG  | Source documents  | Source documents/CRF and clinically significant results are documented on CRF   |
| CT Scan  | Source documents (CD
and printed radiology
reports) | Performance date is captured on CRF   |
| Ultrasound   | Source documents  | Performance date is captured on CRF   |
| Cryoablation   | Source documents  | Performance date is captured on CRF   |
| Biopsy   | Source documents
(Pathology reports)                   | Performance date is captured on CRF   |
| Clinical Laboratory
Reports (CBC, CMP,
CRP, coagulation) | Source documents
(Printed report forms)                | Performance date and clinically
significant results are documented on
CRF |
| Pregnancy test   | Source documents  | Performance date is captured on CRF   |
| Autoimmune profile   | Source documents  | Performance date and clinically   |

#### Table 10 Source vs. CRF Data

| Type of Data   | Source/CRF  | Comment   |
|--|---|---|
|  | (Printed report forms)                                    | significant results are documented on CRF                                       |
| Research blood
(Cytokines and
TH1/TH2 balance) | Source documents
(Printed report forms)                | Performance date and clinically
significant results are documented on
CRF |
| HLA Test   | Source documents and CRF                                  |   |
| Date & time of blood sampling                        | Source documents
(Printed report forms)                | Dates are documented on CRF   |
| Study drug
administration details                 | Source Documents
(Drug administration
Form) and CRF |   |
| Drug accountability                                  | Folder in Pharmacy/
Investigator's Site File           |   |
| HRQoL Questionnaires                                 | CRF   |   |
| Adverse events                                       | Source documents and CRF                                  |   |
| Concomitant
Medication                            | Source documents and CRF                                  |   |
| Protocol Deviations                                  | Source documents  |   |
| Trial Termination details                            | CRF   |   |

The ICF will include a statement by which the subject allows the Sponsor, or designee, the Ethics Committee (IRC/IEC), and the regulatory authorities to have direct access to source data which supports the data on the CRFs (e.g. subject's medical file, appointment books, original laboratory records, etc.).

It is the responsibility of the investigator to maintain adequate and accurate CRFs to record all observations and other data pertinent to the clinical investigation.

The Clinical Monitor (CM) is responsible for performing on-site monitoring at regular intervals throughout the study to verify adherence to the protocol; verify adherence to local regulations on the conduct of clinical research; and ensure completeness, accuracy, and consistency of the data entered in the CRF.

Data review may generate requests for clarifications (Queries) from the Sponsor to which the investigator is obliged to respond by confirming or modifying the data questioned.

# 17.10.2. Electronic Data Capture

If Electronic Data Capture (EDC) will be used for electronic data acquisition and storage, electronic case report forms (eCRFs) will be provided for transfer of all research data by site personnel from data source documentation to a computer database. Each responsible person at a site will have user access with a unique username and password, with permissions providing each person their needed access. Some personnel will have data entry, data review, and query resolution permissions, while others may only have data read permissions, based on their individual trial roles.

CMs will verify all computerized data against its source. Monitoring will be enhanced by computer assisted data management, identifying missing or possibly erroneous data as soon as data are computerized. This approach will allow initial remote monitoring, and communication between CMs and site personnel before and between site visits, and will expedite data review and cleaning. As each subject's data computerization is completed and fully monitored with all queries resolved, that subject's data set will be locked by the CM to only allow read access for the remainder of the trial.

All trial data are to be housed in a secure computing environment. The EDC system will include a complete audit trail of all data entry, monitoring, and query activity that is compliant with HIPAA (and/or equivalents at each participating country) and meets all requirements for 21 CFR Part 11.

Trial data as required by CMs, other authorized representatives of the Sponsor, and appropriate regulatory authority inspectors will be available through the EDC.

All required trial information must be entered into the EDC system. eCRFs are considered complete when all data fields are complete and acknowledged as correct by the CM. In addition, the investigator, as the person ultimately responsible for the accuracy of all CRF data, must sign the investigator's statement at trial completion for each subject.

Final monitored and/or audited eCRFs will be provided by the Sponsor to the sites at the end of the study in the format of PDF file.

## **17.11. STUDY DOCUMENTS**

# 17.11.1. Curricula Vitae

An updated copy of the curriculum vitae limited to the experience, qualification and training for the investigator and sub-investigators (and completed FDA 1572 form and Financial Disclosure Forms) will be maintained with the site regulatory documents.

# 17.11.2. Financial Disclosure

Financial disclosure information must be provided by all investigators and sub-investigators and will be collected by the Sponsor prior to the start of the study.

#### 17.11.3. Archiving of Documents

ICF, source documents, drug accountability and retention records, and other study related documents will be retained in the permanent archives of the study site. These will be available for inspection at any time by the FDA per 21 CFR 312. Records retention for this study is required for a period of 2 years following the date on which this study agent is approved by the FDA for the marketing purposes; or, if no application is to be filed or if the application is not approved for such indication, until two years following the date on which the entire study is completed, terminated, or discontinued, and the FDA is notified.

## **19. APPENDICES**

#### **APPENDIX 1** BIOPSY, CRYOABLATION SURGICAL PROCEDURE

Subjects will be referred to a sponsor dedicated radiology center for the cryoablation and voluntary biopsy procedures and intratumoral injections.

Preferably, the lesion selected for biopsy will not be the same lesion as is targeted for ablation. However, if a second lesion is not available then the lesion for ablation will be biopsied prior to ablation. The cryoablation and biopsy procedures are conducted under CT and/or ultrasound guidance. Visual documentation of probe placement for the cryoprobe probe will be provided and placed in the source documents. In addition, visual documentation of the kill zone after the ablation will also be provided for cryoablation. The tumor biopsy specimen will be placed in formalin in a pre-labeled specimen container. The tumor biopsy specimen will be sent to the Sponsor for pathological analysis.

Subjects will have a target tumor lesion cryoablated under local or conscious sedation followed by an intratumoral AlloStim® injection at a dose of  $1 \times 10^7$  cells formulated in 1 ml of Plasma-LyteA/1% HAS or  $3 \times 10^7$  cells formulated in 3 ml of Plasma-LyteA/1% HSA. The intent of the ablation procedure is not to completely ablate the target lesion, but only to cause an area of necrosis within the tumor. Therefore, it is not necessary to have perfect margins. The intratumoral injection will occur after the ablation area has warmed to  $37^{\circ}$ C.

It is preferred that an interventional radiologist, CT technician, and physician trained in anesthesia or emergency medicine be present during the procedure. A Registered Nurse (RN), medical assistant and a cryoablation technician should also be present to support these procedures (same individual may function in two of these roles). The Sponsor may also have a medical/scientific consultant present. If the ablation target is in or near the lungs, it is recommended that the procedure be conducted in a hospital or near a hospital with the capability to diagnose and treat pneumothorax or related complications.

Cryoablation will be performed by a licensed interventional radiologist or other experienced physician using a CryoCare-28 Percutaneous Probe System (Endocare, CA, USA) or the SeedNetTM System (Galil Medical, Israel). Generally, the Galil system is preferred for approach of lesions in the lungs due to the smaller 17g probe size having less of a chance of pneumothorax complications. These systems use the Joule-Thomson effect to cool the end of a cryoprobe in a closed system. In accordance with the gas coefficient and the dimension of the nozzle, different gaseous elements generate different thermal exchange events at the area close to the nozzle. Argon gas is used for cooling (-187C), and helium is used for heating (67C).

Subjects will be observed for 1-4h prior to release.

#### **Pre-Procedure Assessments**

Subjects may be hydrated prior to the procedure with normal saline or equivalent. All subjects requiring IV conscious sedation will have a pre-procedure assessment which will be documented in the medical records including:

• A medical evaluation (history and physical based) by the interventional radiologist (this should include documentation of current medications and a history of any adverse or allergic drug reactions, including anesthesia or sedation, other allergies, NPO status, and an ASA assessment).

- Assessment of the subject's ability to tolerate conscious sedation
- Review of laboratory studies including coagulation studies. PT/PTT within normal range and INR must be ≤ 1.5. Review with subject the previously signed informed consent for the procedure and plan for sedation.
- Age appropriate assessment, including baseline set of vital signs and a pre-procedure SPO2.
- Note that subjects exhibiting hemodynamic instability, oxygen desaturation, or respiratory depression/failure are not appropriate candidates for IV conscious sedation.

Any of the following drugs (or combination) can be used for conscious sedation at the discretion of the treating physician and administered intravenously (IV) or intramuscularly (IM):

- Diazepam (Valium) adult dose: 2-10 mg.; >60yo: 2-5 mg
- Lorazepam adult dose: 0.5 mg/kg; >60yo: .02-0.05 mg/kg
- Midazolam (Versed) adult dose: .07 0.08 mg/kg; >60yo: .02-0.05 mg/kg
- Morphine adult dose: 0.025-0.2 mg/kg; >60yo: 0.05-0.2 mg/kg (Max. of 15 mg)
- Meperidine (Demerol) adult dose: 1-1.5 mg/kg; >60yo: 1-1.5 mg/kg
- Fentanyl (Sublimaze) adult dose: 1-2 mcg/kg; >60yo: 1 mcg/kg

Care must be taken to assure that the total dose does not obtund protective pharyngeal reflexes or render the subject unresponsive to verbal stimuli.

For some procedures, where subject breath movements may affect the ability to accurately place the cryoprobe,  $DIPRIVAN^{\text{(B)}}$  (propofol) or similar sedation medication is allowed during the interval of probe placement.

The following equipment/emergency drugs shall be immediately available (Code Cart) prior to IV conscious sedation being administered:

- Oxygen source
- Ambu bag
- Laryngoscope
- Endotracheal Tubes (i.e. sizes 5.0 mm, 6.0 mm, 7.0 mm, 8.0 mm)
- Oral and nasal airways
- Emergency drugs (Narcan, Romazicon)
- Cardiac monitor/defibrillator and suction equipment
- Pulse Oximeter

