## 6.1.2. Cryoablation

The cryoablation procedure is conducted with U.S. FDA approved medical devices and disposable probes as an out-patient procedure. Local and/or conscious sedation is allowed. These treatments are used to kill tumor cells. Cryoablation is a minimally invasive treatment that involves placing a probe into a known tumor percutaneously under image guidance (e.g. CT scan or Ultrasound). The cryoablation procedure should be conducted by a licensed interventional radiologist approved by the Sponsor. Unlike normal ablation methods that seek to ablate all viable tumor and leave no tumor at the margins, the ablation procedure for this protocol should aim to ablate only a portion of the tumor and leave viable tumor margins. Effort should be made to ablate viable tumor and avoid necrotic areas of the tumor. Thus, the edge of the tumor, rather than the center is a preferred target. Intratumoral injection of study drug is best accomplished by first inserting a guide device with a gauge larger than the cryoprobe. Generally, a 14g guide is suggested. In this manner, biopsy tools and the cryoprobe can be inserted through the guide to reach the tumor. On site pathology or radiological confirmation that the guide is inserted within viable tumor is preferred. The ablation should occur with at least two freeze-thaw cycles each of at least 10 minutes. The study drug should only be injected when the temperature is verified to be above  $35^{\circ}$  C. The study drug is best delivered using a needle that has side ports to assure the drug is delivered within the ablated lesion and not injected through the lesion into the normal tissue. After the ablation, the guide

tract should be sealed with mesh material to prevent bleeding. All subjects should be observed for at least 2 hours following the procedure for any signs of bleeding or other adverse events. Subjects should be monitored continuously for pulse, respiration, blood pressure and oxygen saturation during the procedure. The type of probes used, the location of the tumor, the amount of tumor ablated, the cooling and warming cycle times, vital signs and procedure notes should be documented in source medical records.

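### Appendix 1 prints an adult lorazepam dose 10 to 25 times the over-60 dose, an outlier that looks like a decimal slip in a sedation instruction

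*Combined protocol and SAP*

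**What the plan says.** Appendix 1, under Pre-Procedure Assessments, lists six drugs for intravenous or intramuscular sedation, each with an adult dose and a dose for subjects over 60. The lorazepam entry is "Lorazepam adult dose: 0.5 mg/kg; >60yo: .02-0.05 mg/kg". Two other benzodiazepines are listed: "Midazolam (Versed) adult dose: .07 0.08 mg/kg; >60yo: .02-0.05 mg/kg" and "Diazepam (Valium) adult dose: 2-10 mg.; >60yo: 2-5 mg". Morphine, meperidine and fentanyl complete the list. Morphine is the only drug with a maximum in mg (15 mg). Lorazepam appears nowhere else in the documents.

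The list is permissive: "Any of the following drugs (or combination) can be used for conscious sedation at the discretion of the treating physician". It is followed by a general limit on effect: "Care must be taken to assure that the total dose does not obtund protective pharyngeal reflexes or render the subject unresponsive to verbal stimuli". Reversal agents must be at hand: "Emergency drugs (Narcan, Romazicon" are among the items required on the code cart.

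Sedation is an option. Section 6.1.2 says "Local and/or conscious sedation is allowed", and Appendix 1 says "Subjects will have a target tumor lesion cryoablated under local or conscious sedation". Section 10.2 admits subjects aged 18 to 80, so both age columns can apply.

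**The concern.** A lower sedative dose for older patients is ordinary, so a gap between the two columns is no error in itself. What stands out is the size of this gap within a single list. The adult lorazepam figure is exactly ten times the upper end of the over-60 range, which is the pattern a misplaced decimal point leaves.

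At stake is a sedative dose that a site may take from the protocol for a percutaneous liver procedure. If the adult figure is ten times too high, the printed dose for subjects aged 60 or under is ten times the intended one. If the over-60 range is ten times too low, the printed dose for older subjects is a tenth of the intended one. Drugs may be combined, and the line has no maximum in mg.

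**Working it through.** The plan states the doses but no ratio, so there is no derived figure to reproduce. The check compares the adult dose with the over-60 dose for every drug in the list.

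Inputs are the six lines in Appendix 1, Pre-Procedure Assessments. Adult is read as age 60 or under. The midazolam adult entry is read as the range 0.07 to 0.08 mg/kg, because a hyphen appears to be missing in the extracted text.

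Smallest ratio = lowest adult dose / highest over-60 dose. Largest ratio = highest adult dose / lowest over-60 dose.

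| Drug | Adult | Over 60 | Smallest ratio | Largest ratio |
|---|---|---|---|---|
| Diazepam (mg) | 2 to 10 | 2 to 5 | 2/5 = 0.4 | 10/2 = 5.0 |
| Lorazepam (mg/kg) | 0.5 | 0.02 to 0.05 | 0.5/0.05 = 10 | 0.5/0.02 = 25 |
| Midazolam (mg/kg) | 0.07 to 0.08 | 0.02 to 0.05 | 0.07/0.05 = 1.4 | 0.08/0.02 = 4.0 |
| Morphine (mg/kg) | 0.025 to 0.2 | 0.05 to 0.2 | 0.025/0.2 = 0.125 | 0.2/0.05 = 4.0 |
| Meperidine (mg/kg) | 1 to 1.5 | 1 to 1.5 | 1/1.5 = 0.67 | 1.5/1 = 1.5 |
| Fentanyl (mcg/kg) | 1 to 2 | 1 | 1/1 = 1.0 | 2/1 = 2.0 |

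**Against the whole list.** Lorazepam's smallest ratio is twice the largest ratio of any other drug (10/5 = 2.0). Comparing upper limits only, lorazepam gives 10, diazepam and fentanyl 2.0, midazolam 1.6, and morphine and meperidine 1.0.

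**Against the closest comparator.** Midazolam is also a benzodiazepine dosed in mg/kg, with an identical over-60 range. Lorazepam's smallest ratio is 2.5 times midazolam's largest (10/4 = 2.5). Taking either midazolam adult figure alone keeps its ratio within 1.4 to 4.0, so the missing hyphen does not affect this.

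**Fall at the age step.** Lorazepam: 1 - 1/10 = 90% to 1 - 1/25 = 96%. Midazolam: 1 - 1/1.4 = 29% to 1 - 1/4 = 75%. The largest fall for any other drug is diazepam's, 1 - 1/5 = 80%.

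**In mg, at assumed weights.** At 70 kg, adult lorazepam is 0.5 x 70 = 35 mg; over 60 it is 0.02 x 70 = 1.4 mg to 0.05 x 70 = 3.5 mg. Over 50 to 100 kg, the adult dose runs from 25 to 50 mg and the over-60 dose from 1.0 mg (0.02 x 50) to 5.0 mg (0.05 x 100).

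**If one figure is out by ten.**
- Adult figure 0.05 mg/kg: ratio 0.05/0.05 = 1.0 to 0.05/0.02 = 2.5; at 70 kg, 3.5 mg against 1.4 to 3.5 mg.
- Over-60 range 0.2 to 0.5 mg/kg: ratio 0.5/0.5 = 1.0 to 0.5/0.2 = 2.5; at 70 kg, 35 mg against 14 to 35 mg.

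Both corrections bring lorazepam into line with the rest of the list, so the arithmetic cannot choose between them.

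**The case against.** **Different age groups.** The figures apply to different subjects, so a reader might infer that the protocol contradicts itself or contains a failed calculation. It does neither. The evidence is an outlier and no more. Nothing in the documents says that age reductions should be similar across drugs, and the list is not a uniform scheme: morphine's lower limit is higher above 60 than for adults, and meperidine does not change. That is fair, but lorazepam remains the outlier on every pairing, including against the drug with the same over-60 range.

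**Extraction.** The line was read from a PDF by a program. The neighboring midazolam line seems to have lost a hyphen, and other dose expressions were altered (in Section 14.4.3 a multiplication sign became a greater-or-equal sign). A zero lost from the adult figure is possible and would dissolve the point. It has not been shown: 0.05 was read intact three times in this list, once on the lorazepam line itself. The risk is a reason to check the source first.

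**Safeguards.** Sedation is optional and nobody has to choose lorazepam. A medical evaluation precedes sedation, a physician orders the drug and gives the first dose, and a physician trained in anesthesia or emergency medicine is preferred. Cardiac rhythm and oxygen saturation are monitored continuously, and the case stops on persistent desaturation. All of this stands and lowers the likelihood of harm. None of it supplies a numeric limit for lorazepam or identifies the right figure, and a nurse may give the later doses.

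**Conclusion.** The point holds as a suspected decimal error in an operative sedation instruction. The adult lorazepam dose is 10 to 25 times the over-60 dose, in a list where no other drug exceeds 5. It should be fixed if the source confirms the line. Confidence is medium, because the conclusion rests on the extracted line being faithful, on reading adult as age 60 or under, and on comparison within the list. The mg figures also rest on assumed body weights.

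Three stronger readings are not supported:
- That the adult figure is the wrong one and 0.05 mg/kg was meant. A slip in the over-60 range fits equally well, and no other section settles it.
- That subjects will receive 35 mg. This is what the line yields at 70 kg if applied literally; it does not predict exposure, and the documents do not say how often sedation or lorazepam will be used.
- That the trial's results are affected. No endpoint, sample size or analysis depends on this line.

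**What to change.** 1. Compare the lorazepam line with the source PDF. If it shows a different figure consistent with the over-60 range, the point closes and the plan needs no change.
2. If it reads 0.5 mg/kg, tell the site not to use the lorazepam line. The other five listed drugs remain, and choosing among them is already within the physician's discretion.
3. Have a qualified anesthesia or pharmacy reviewer supply the correct figures for both age groups. No dose is proposed here.
4. Correct Appendix 1 by amendment, following Section 17.4.

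The cost is a source check and, if confirmed, a site notice, one sedative temporarily unavailable, and a one-line amendment.
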